#### Sub Study:

##### Alcohol and HIV

Globally, an estimated 2.3 billion people aged  $\geq 15$  years (43% of this population; 32% in Africa) take alcohol, while harmful use of alcohol was responsible for about 3 million deaths in 2016. Alcohol use is prevalent among PLHIV and in sub-Saharan Africa the region with the highest population of PLHIV this higher prevalence of alcohol use in this population has been well documented. Further, alcohol use has been associated with male gender, cigarette smoking, alcohol use in the family, missed ART, mental distress, low CD4+ cell count and low income. Alcohol use among PLHIV interferes with adherence to ART and retention in HIV care, which negatively affects viral suppression. Harmful use of alcohol has also been shown to be associated with increased toxicity from ART, lower CD4+ cell count, increased opportunistic infections due to compromised immunity and higher resistance to ART.

##### Alcohol and Non-communicable Diseases

The global increase in morbidity and mortality from NCD in low-, middle- and high-income countries is alarming. In 2016, alcohol use caused 1.7 million deaths (4.3% of NCD deaths) and 65.5m disability adjusted life years. Alcohol consumption is associated with increased risk of cancers including liver, oral and pharyngeal cavity, esophageal, colon, rectal, breast and gallbladder and cardiovascular diseases (CVDs). In 2016, 0.4 million of the 9 million cancer deaths were attributed to alcohol use. Similarly, alcohol use caused 0.6 million of the CVD-related deaths (3.3% of CVD deaths). Harmful alcohol consumption amongst PLHIV may further aggravate to the increased risk of NCD even among stable virally suppressed PLHIV on ART. The need to address this emerging trend in NCDs is paramount so as not to lose the gains made in fighting the HIV scourge and providing PLHIV with quality long life.

##### Co-occurrence of alcohol and tobacco use among PLWH in Kenya

The concomitant use of alcohol and cigarette is high in the general population and among PLHIV. Although precise prevalence estimates of alcohol and smoking among PLWH are lacking in Kenya, the Kenyan Ministry of Health STEPWISE Survey 2015 (a nationally representative household survey of 4203 adults aged 18-69 years conducted in Kenya between April and June 2015) reported tobacco use to be strongly and significantly associated with higher odds of heavy alcohol consumption (unadjusted OR 6.9, 95% CI 4.4-10.8—tobacco users compared to non-tobacco users). Yet, Kenyans generally hold positive attitudes towards consumption of substances such as cigarettes (73%), packaged liquor (72%), traditional brew (69%), and other tobacco products (68%). These positive attitudes may severely underestimate the risk of cancer associated with using alcohol and tobacco together.

##### Behavioral interventions for alcohol cessation

Behavioral interventions including brief interventions and cognitive behavioral therapy, have been used to help reduce alcohol use among PLHIV with promising results

We published a systematic review and meta-analysis in JAIDS representing 1822 subjects from these eight smoking cessation studies. We found a statistically significant

effect of behavioral interventions compared to control in increasing abstinence in HIV-infected smokers with a moderate effect size RR 1.51 (95% CI 1.17, 1.95). Of note, those studies with interventions of  $\geq 8$  sessions (such as the intervention we will be using: Positively Smoke Free) had a large effect size for the abstinence endpoint RR 2.88 (95% CI: 1.89-4.61).

4 \* **Provide the scientific or scholarly background, rationale, and significance of the research and how it will add to existing knowledge:**

Smoking Rates among People Living with HIV/AIDS are Alarmingly High: Smoking is the leading preventable cause of death and disease in the developed nations. Worldwide estimates, albeit largely from cohorts in the developed world, suggest that people living with HIV/AIDS (PLWH) smoke at nearly three times the rate of the general population. These extraordinary smoking rates are associated with greater AIDS related morbidity 31, greater non-AIDS related morbidity (including non-AIDS cancers, cardiovascular disease, and pulmonary disease) and greater mortality. Smoking significantly impacts the progression and outcome of HIV disease, and has been identified as the leading contributor to premature mortality among people with HIV. In fact, a study from Denmark estimated that HIV-positive individuals lose more years from smoking than from HIV infection in and of itself. In our view, shared by others in the field 20, effective tobacco treatment strategies in the US would be the single most impactful intervention to improve survival in PLWH. A recent modeling study completed at Harvard estimated that an intervention with 10-25% in the US efficacy would save 106,000-265,000 life years. As the reach of antiretroviral therapy (ART) improves throughout Africa, and life expectancies of PLWH improve there, the importance of tobacco use as a proximate and leading cause of morbidity and mortality is bound to escalate as will the need for effective tobacco treatments. Most PLWH who smoke want to quit. Although many interventions are effective in helping general population smokers quit, research examining outcomes of smoking cessation treatments for PLWH is limited to high income countries. To what degree these data translate to lower-income countries that may have greater challenges with health care infrastructure, resources and medication access is not clear. Thus, establishing the efficacy of interventions that are accessible to PLWH who reside in lower-middle income countries is of critical importance.

sub study:

Alcohol and HIV

Globally, an estimated 2.3 billion people aged  $\geq 15$  years (43% of this population; 32% in Africa) take alcohol, while harmful use of alcohol was responsible for about 3 million deaths in 2016. Alcohol use is prevalent among PLHIV and in sub-Saharan African the region with the highest population of PLHIV this higher prevalence of alcohol use in this population has been well documented. Further, alcohol use has been associated with male gender, cigarette smoking, alcohol use in the family, missed ART, mental distress, low CD4+ cell count and low income. Alcohol use among PLHIV interferes with adherence to ART and retention in HIV care, which negatively affects viral suppression. Harmful use of alcohol has also been shown to be associated with increased toxicity from ART, lower CD4+ cell count, increased opportunistic infections due to compromised immunity and higher resistance to ART.

Alcohol and Non-communicable Diseases

The global increase in morbidity and mortality from NCD in low-, middle- and high-income countries is alarming. In 2016, alcohol use caused 1.7 million deaths (4.3% of NCD deaths) and 65.5m disability adjusted life years. Alcohol consumption is associated with increased risk of cancers including liver, oral and pharyngeal cavity, esophageal, colon, rectal, breast and gallbladder and cardiovascular diseases (CVDs). In 2016, 0.4 million of the 9 million cancer deaths were attributed to alcohol use. Similarly, alcohol use caused 0.6 million of the CVD-related deaths (3.3% of CVD deaths). Harmful alcohol consumption amongst PLHIV may further aggravate to the increased risk of NCD even among stable virally suppressed PLHIV on ART. The need to address this emerging trend in NCDs is paramount so as not to lose the gains made in fighting the HIV scourge and providing PLHIV with quality long life.

Co-occurrence of alcohol and tobacco use among PLWH in Kenya

The concomitant use of alcohol and cigarette is high in the general population and among PLHIV. Although precise prevalence estimates of alcohol and smoking among PLWH are lacking in Kenya, the Kenyan Ministry of Health STEPWISE Survey 2015 (a nationally representative household survey of 4203 adults aged 18-69 years conducted in Kenya between April and June 2015) reported tobacco use to be strongly and significantly associated with higher odds of heavy alcohol consumption (unadjusted OR 6.9, 95% CI 4.4-10.8—tobacco users compared to non-tobacco users). Yet, Kenyans generally hold positive attitudes towards consumption of substances such as cigarettes (73%), packaged liquor (72%), traditional brew (69%), and other tobacco products (68%). These positive attitudes may severely underestimate the risk of cancer associated with using alcohol and tobacco together.

Behavioral interventions for alcohol cessation

Behavioral interventions including brief interventions and cognitive behavioral therapy, have been used to help reduce alcohol use among PLHIV with promising results

We published a systematic review and meta-analysis in JAIDS representing 1822 subjects from these eight smoking cessation studies. We found a statistically significant effect of behavioral interventions compared to control in increasing abstinence in HIV-infected smokers with a moderate effect size RR 1.51 (95% CI 1.17, 1.95). Of note, those studies with interventions of  $\geq 8$  sessions (such as the intervention we will be using: Positively Smoke Free) had a large effect size for the abstinence endpoint RR 2.88 (95% CI: 1.89-4.61).

## Study Procedures

**If you uploaded a separate research protocol document in the 'Research Protocol' page, cite the applicable section and page numbers from that document in the answer boxes below. (If this study is a collaborative UM/VA study please list each procedure that is being conducted and the locations where it is being conducted.)**

1 \* Describe all procedures being performed for research purposes only (these procedures would not be done if individuals were not in the study) and when they are performed, including procedures being performed to monitor subjects for safety or to minimize risks:

Formative Sessions:

Prior to starting the main study, we will interview a set of individuals currently attending one of the recruitment clinics. The interview will either be a focus group (of about 8-10 individuals) or a stand alone interview. The purpose of the formative sessions is to learn about the population and ensure our study intervention and study guidance is appropriate for our audience.

Screening:

Screening will consist of a chart review for medical history. Additional screening questions will include: MINI International Neuropsychiatric Interview (Sections: Alcohol, Drug, and Suicide ), Readiness to Quit Ladder, and Hopkins HIV Dementia Scale. Expired air CO will be assessed with using a Smokerlyzer-Breath Carbon Monoxide Monitor.

Baseline and Evaluation Phase (EP):

Upon completion of the consent and screening process, participants will enter the evaluation phase in which they will provide a thorough medical history including documentation of all medications including antiretroviral medication (via review of medical record) and complete a physical assessment- including vital signs--blood pressure, heart and respiratory rates, height and weight.

If a potential participant has been evaluated clinically within the last month, the research clinician may choose to rely on data from that evaluation per their clinical judgement and their clinical impression of need for replication of this data for the purpose of the eligibility evaluation. This would not include vital signs.

Pregnancy Testing:

Female participants who have the potential to become pregnant will have a pregnancy test during the evaluation phase and approximately monthly during the study (while taking study medication). They will be asked to use acceptable method of contraception during the medication phase of the study (week 1-12). Participants will sign a contraception consent to confirm their agreement (In the baseline packet). Condoms will also be provided at research appointments.

Baseline Interview:

Participants will also complete a series of assessment questionnaires (baseline interview). Vital signs will also be recorded. Only those continuing to meet full inclusion criteria and do not meet exclusion criteria will proceed to randomization and remain in the study. The list of assessments to be completed are located in the study schedule in the Additional Documents section.

Randomization

Study participants who are deemed eligible for the study will complete baseline testing and will then be randomized 1:1:1:1 to four study conditions: (1) Bupropion + PSF; (2) Bupropion + SOC; (3) Placebo + PSF; (4) Placebo + SOC. Participants will be randomly assigned to one of the four conditions using permuted blocks which will randomly vary in size. The research pharmacy will be notified of the drug randomization (Bupropion or placebo). All raters, investigators, and other staff will be blind to treatment assignment except for the dispensing pharmacist. Separate emergency unblinding envelopes for each participant will be kept in a locked cabinet at the dispensing pharmacy in the case of a medical emergency. All participants who are randomized will be taught the correct use of the study medication, and assisted in setting a quit date with the instruction to quit on approximately Day 8 (beginning of Week 2) following one week of medication.

Medication Intervention:

PSF is an intensive, tailored, social cognitive theory-driven intervention that promotes cessation in PLWH smokers. Its development was guided by previous pilot work characterizing the sociobehavioral drivers of tobacco use in PLWH 40. It is an 8-session program, with session lengths ranging from 45-60 minutes. A syllabus serves as a guide for therapists. The course content has gone through multiple rounds of revision in response to input from intra and extra-institutional experts in HIV and smoking cessation, PLWH smokers, and the ID Clinic community advisory board. Themes of particular relevance to HIV-infected smokers permeate the course content, and the heterogeneity of the PLWH community and how this relates to smoking behaviors (i.e. similarities and differences between drug users, LGBT, and depressed individuals) is highlighted. The "microtargeting" of these subsets of PLWH has received the praise of group participants. An overview of the course content, including tailoring themes, has been previously published. All treatment sessions are audiotaped. If a participant misses an intervention session, we will call him/her to reschedule. If the participant is having difficulty attending some of the sessions in person, we will offer to conduct them over the telephone.

Control Condition

Those randomized to standard of care will receive of standard of care smoking cessation treatment by a trained research assistant at the time of randomization. Participants will be given a quit smoking brochure and brief advice to quit (i.e. < five minutes)

Follow Up Assessment Interviews:

All participants will be re-assessed at approximately week 12 and approximately week 36. Vital signs will also be recorded. All assessments will be administered in a confidential and private location by experienced research assistants who are masked to the results of randomization. The list of assessments to be completed are located in the study schedule in the Additional Documents section.

Participants will also complete a brief visit when they return at week 1, 2, 4, and 8 for their medication refill. All participants will complete vital signs as well as answer a few questions about their medication side effects (if any), medication adherence, their mood and smoking status.

**Expired carbon monoxide (CO):**

Expired air CO provides an accurate indirect measure of carboxyhemoglobin (COHb) level and is a standard biochemical method for assessing a smoker's level of intake. According to the SRNT Subcommittee on Biochemical Classification report, measuring CO provides a sensitivity and specificity of approximately 90% for current tobacco use. Expired air CO will be assessed with using a Smokerlyzer-Breath Carbon Monoxide Monitor.

Expired CO will be monitored at each visit (Screening, Evaluation Phase, Baseline, week 1, 2, 4, 8, 12, and week 36).

Implementation Costs Assessment is to estimate the organizational costs of implementing Positively Smoke Free services, using data from the study site. Data for the implementation costs assessment component will include the amount of personnel time spent completing each step in the Positively Smoke Free implementation process, including all training and supervision activities and all meetings required to set up Positively Smoke Free services. Personnel time will be multiplied by appropriate wage rates (i.e., the salary cost per hour or per year) for each person, and then fixed percentages will be added to account for additional personnel costs 28. The time use data for this component will come from project records of training meeting attendance and meeting duration as well as from a brief time use survey of personnel involved in delivering the intervention. Provider organizational and administrative expenses associated with the implementation process, such as the time costs of managing implementation activities and any friction costs associated with having to adapt to new workflow processes, will be included in implementation costs. These organizational/administrative implementation costs will be identified from qualitative interviews conducted with key informants (i.e., senior clinic administrators) at the study site, and then estimated based on clinic accounting records or based on imputed cost estimates, using standard economic cost imputation approaches 28adapted for the Kenyan context. The qualitative interviews will allow us to gain insight into the specific workflow or administrative changes that may have been required to implement Positively Smoke Free services. Other implementation resources may include clinic space and associated utilities, software licensing fees, computer use, and supplies. We will maintain detailed project records of these expenses or, as in the case of room space, we will create imputations in the standard ways based on the notion of resource opportunity cost 28. All cost estimates will be appropriately time-discounted and inflation-adjusted 28. The planned assessment will yield rigorously obtained approximations of total implementation costs at a new site of care. We will share these estimates in an annual project report to NIH and will also share them with our partners in Kenya.

**Sub Study:**

**Procedures:**

Create culturally congruent health education materials around cancer-related risks of tobacco and alcohol co-use to populations at high risk for the two behaviors such as PLWH who smoke in Kenya.

This will be completed by conducting focus groups and in-depth interviews with key informants, to evaluate understanding and acceptance of these educational materials, and iteratively update the Positively Smoke Free (PSF) syllabus to ensure maximal impact.

The proposed work will add a previously standardized group of questions to evaluate awareness of the link between alcohol and cancer at each of the parent study visits. These questions evaluated comparing baseline to 12-week follow-up and 36-week follow-up, will help to determine the extent, if any, the new material added to the PSF syllabus changes awareness of the link between alcohol and tobacco use and cancer.

The participants will be recruited from HIV clinics in Nairobi, Kenya. This protocol will use consent forms from the University of Nairobi. Their drafted consent forms are uploaded in the Additional Documents section. The results of this study will provide policymakers, community leaders and clinicians with critical evidence of the most effective alcohol and smoking cessation treatments for PLWH.

We are looking to consent approximately 70 individuals to either:

Option 1: Participate in a one time feedback group with other individuals who use alcohol – called a focus group (Topic questions are uploaded in the focus group section)

OR

Option 2: Participate in a one time private interview where the individual will have a one on one interview with a trained interviewer in a private area. (Interview questions are uploaded into the survey section)

Each option will take approximately 1 hour plus the time for consenting procedures.

The group discussion and the one on one interview will be audio-taped. The audio-tape will be used only by the research team to ensure we captured all information provided by the participants. The audio-tape will not be used for commercial or teaching purposes and will be destroyed at the end of the project.

**2 \* Describe all procedures already being performed for diagnostic or treatment purposes (if not applicable to the study, enter "N/A"):**

n/a

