**1 \* Describe the purpose, specific aims, or objectives of this research. State the hypothesis to be tested:**

Primary Aim 1: Compare bupropion therapy to placebo on rates of 7-day point prevalence abstinence (PPA) at 36 weeks in smokers with HIV/AIDS. We hypothesize that rates of smoking abstinence at week 36 will be higher in those treated with bupropion compared to placebo.

Primary Aim 2: Compare Positively Smoke Free to low intensity, brief counseling on rates of 7-day PPA at 36 weeks in smokers with HIV/AIDS. We hypothesize that rates of smoking abstinence at week 36 will be higher in those treated with Positively Smoke Free compared to brief counseling.

Primary Aim 3: Compare Positively Smoke Free + bupropion to the other two study conditions outlined above on rates of 7-day PPA in smokers with HIV/AIDS at 36 weeks. We hypothesize the effect of Positively Smoke Free with bupropion therapy is greater than the effect of Positively Smoke Free or bupropion therapy alone.

Secondary Aim: Estimate the organizational costs of implementing Positively Smoke Free, bupropion or both. All cost estimates will be appropriately time-discounted and inflation-adjusted. The planned assessment will yield rigorously obtained approximations of total implementation costs at a new site of care.

Exploratory Aim: Explore whether the effect of PSF compared to brief counseling with bupropion is greater than the effect of PSF without bupropion.

Given the critical need for information about the up-front expenses required to implement smoking cessation services in Kenya, we plan to conduct an implementation costs assessment to provide rigorously obtained approximations of total implementation costs of each intervention tested in this trial.

Sub Study:

AIM 1: Develop, culturally adapt and update the PSF intervention in the main study to include educational material about the cancer risk associated with tobacco and alcohol use.

AIM 2: Preliminarily determine the extent the updated PSF syllabus changes awareness of the link between alcohol and tobacco use and cancer.

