We propose to randomize 300 participants to one of the following 4 conditions: (1) bupropion + Positively Smoke Free (an 8 session tailored behavioral intervention for PLWH smokers); (2) bupropion + Standard of Care (brief advice to quit); (3) Placebo + Positively Smoke Free; and (4) Placebo + Standard of Care. Given the factorial nature of the design, we will be able to assess the main effect of bupropion vs. Placebo, Positively Smoke Free vs. Standard of Care, and the additive effect of those two treatments. We chose to use a factorial design as it is a highly efficient method of assessing multiple treatments in a single trial with the possibility of saving both time and resources. All participants will be assessed at baseline, 12 weeks and 36 weeks (6 months post study completion).

Participants will be randomly assigned to one of the four conditions using permuted blocks which will randomly vary in size. The research pharmacy will be notified of the drug randomization (bupropion or placebo). All raters, investigators, and other staff will be blind to treatment assignment except for the dispensing pharmacist.

Separate emergency unblinding envelopes for each participant will be kept in a locked cabinet at the dispensing pharmacy in the case of a medical emergency. All participants who are randomized will be taught the correct use of the study medication, and assisted in setting a quit date.

Sub study:

There will be no group assignment or randomization.

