**Exploratory Analyses:**

**Other smoking outcomes:** We will use a Generalized Linear Mixed Model (GLMM; Proc MIXED) to assess if the treatment conditions have a significant effect on other smoking outcomes (e.g. number of cigarettes smoked per day) over time. Treatment conditions, time and the interaction of time with the treatment conditions will be included in the model. A random intercept will be used to account for the non-independence of the repeated measures. An unstructured covariance matrix will be employed. Significant effects will be followed up with specific contrast statements.

**Mediation:** We will use Proc Mixed to assess the interventions impact on possible mediating variables for bupropion (craving, withdrawal) and for PSF (self-efficacy, depression, loneliness, substance abuse). Mediators will be assessed at 12 weeks, controlling for baseline. For those variables that are significant we will conduct additional analyses to determine if change in those mediators is related to smoking cessation at 24 weeks. If all conditions are met, we will use the MacKinnon 121 approach to formally assess for mediation of smoking cessation by the targets of the interventions.

**Moderators:** We will assess possible clinical (e.g. depression, smoking severity at baseline, years smoked) and demographic (e.g. age, race) moderators on smoking cessation. We use the analyses described in For Aims 1-3 to assess moderation by including these variables and their interaction with the treatment conditions to the models.

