**Sub Study:**

In order to adapt PSF we will follow recommended methods from Rounsaville's Stage Model of Behavioral Therapy Research. Our group already used similar methods in developing and adapting other behavioral interventions in the context of R34 grants as well as adapting the PSF syllabus for use in Nairobi. The adaptation will allow interventionists and clients at the methadone maintenance clinic an opportunity to review and comment on the format of the manualized intervention and make recommendations regarding treatment content with an eye toward cultural relevance and meaning. All additions to the workbook will be appropriately translated into Swahili with the translation verified by performing an independent back-translation. The updated workbook will be given to a purposive sample of clients and clinicians to review and mark up. We've completed multiple focus groups in the course of our formative work in the trial and are well positioned to complete new ones quickly and well. The results of these in-depth interviews will be summarized and reviewed by Drs. [name], [name] and [name]. Based on the recommendations appropriate changes will be made to the PSF workbook.

We will add a series of standardized questions regarding alcohol consumption (e.g., quantity, frequency, and craving) to better describe the pattern and utilization of alcohol in the study sample. We will also add a series of questions developed by Bukyx et al. to evaluate awareness of the link between alcohol and cancer. All additional questions will be translated into Swahili with the translation verified by performing an independent back-translation. The analysis of change in awareness of the link between alcohol and tobacco use comparing baseline to 12-week follow-up and 36-week follow-up will be conducted by [name], our study statistician, using methods and procedures already described in the parent study. Additionally, we will track longitudinal outcomes of alcohol use over time to determine if alcohol consumption changes as a result of the information provided by the updated PSF syllabus.

Please note:

We have increased the total N from 445 to 650, an increase of about 200. This was done for 2 reasons:

1. We previously added a sub study in a prior modification and did not increase the N at that time because enrollment numbers were lower. We have since then consented several individuals to the sub study and we are close to reaching our current N.

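### The sub-study names no PSF-vs-SOC contrast for cancer-risk awareness or alcohol use; the only comparison written is baseline to follow-up, yet change is to be read as an effect of the updated syllabus

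*Protocol*

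**What the plan says.** Sub-study Aim 2 (Protocol, Justification, Objective, & Research Design, item 1) is causal in form: "Preliminarily determine the extent the updated PSF syllabus changes awareness of the link between alcohol and tobacco use and cancer". It states no comparison.

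The comparison appears in Study Procedures, item 1, Sub Study, and in near-identical words in the Lay Summary: "These questions evaluated comparing baseline to 12-week follow-up and 36-week follow-up, will help to determine the extent" of any change brought about by the added material. The questions are put "to evaluate awareness of the link between alcohol and cancer at each of the parent study visits".

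Sample Size and Data Analysis, item 2, Sub Study, repeats the baseline-to-week-12-and-36 comparison for awareness and says the analysis will be done "using methods and procedures already described in the parent study". Alcohol use is a separate sentence: it is followed over time "to determine if alcohol consumption changes as a result of the information provided by the updated PSF syllabus". That sentence does not point to the parent-study methods. The alcohol consumption questions are meant "to better describe the pattern and utilization of alcohol in the study sample".

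The SAP does not mention the sub-study, awareness or alcohol consumption as outcomes.

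**The concern.** A change from baseline in people who received PSF mixes the effect of the syllabus with everything else that happens over 36 weeks. Being asked repeatedly about alcohol and cancer may raise awareness by itself. Drinking may shift because participants are attempting to quit smoking, because people often enter a study at an unusual point in their drinking, or because of calendar trends. All of these can act in the SOC arm too. If the before-after change is what gets tested, any of them could be reported as an effect of the new syllabus.

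The parent trial offers a better comparison. Participants are randomised 1:1:1:1, so PSF and SOC are allocated equally, and all are re-assessed at weeks 12 and 36. SOC is a brochure and under five minutes of advice. The Lay Summary and Study Procedures say the sub-study results will give policymakers critical evidence on the most effective alcohol and smoking cessation treatments, and an uncontrolled change cannot support that.

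**Working it through.** The plan gives no sample size, effect size or power for Aim 2, so there is no figure of its own to reproduce. The number available from the parent trial does reproduce: 300 × (1 − 0.20) = 240 evaluable, 240/4 = 60 per cell, 240/2 = 120 per PSF or SOC margin, as Sample Size and Data Analysis, item 1, states. Alpha is 0.05, two-sided, from the same place.

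**Before-after test when the syllabus does nothing (binary awareness).** Assume awareness rises by d = 0.10 in both arms. Let ψ be the proportion who change their answer in either direction, assumed 0.20 (15% gain, 5% lose) to 0.30 (20% gain, 10% lose). For the McNemar test,

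Pr(significant) ≈ Φ[(d√n − 1.96√ψ) / √(ψ − d²)]

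- n = 120, ψ = 0.20: (1.095 − 0.877)/0.436 = 0.50, giving 69%.
- n = 120, ψ = 0.30: (1.095 − 1.074)/0.539 = 0.04, giving 52%.
- n = 75 (assumed), ψ = 0.20 and 0.30: −0.02 and −0.39, giving 49% and 35%.

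Both arms have the same expected change, so the PSF-vs-SOC difference is zero on average and its test keeps its nominal 5%.

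**The same check on a continuous score.** Simulation of 4,000 trials, assumed baseline-to-follow-up correlation 0.5, common drift in both arms, no PSF effect:

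| Common drift (assumed) | Before-after in PSF, n = 120 | Before-after in PSF, n = 40 |
|---|---|---|
| 0.1 SD | 20% | 9% |
| 0.2 SD | 58% | 22% |
| 0.3 SD | 90% | 45% |

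Across these rows the PSF-vs-SOC test of change was significant in 4.4-5.5% of runs.

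**What the randomised contrast could detect.** With 80% power, the detectable standardised difference is (1.960 + 0.842) × √(2/n), where n is the number per arm. Baseline adjustment multiplies it by √(1 − r²), which is 0.866 at an assumed r = 0.5. Only 120 comes from the plan; the smaller numbers are assumptions about how many were randomised after the update.

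| Per arm | Unadjusted | Baseline-adjusted, r = 0.5 |
|---|---|---|
| 120 | 0.36 SD | 0.31 SD |
| 60 | 0.51 SD | 0.44 SD |
| 40 | 0.63 SD | 0.54 SD |
| 20 | 0.89 SD | 0.77 SD |

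For a binary answer with an assumed 30% aware under SOC, the detectable PSF rate is 47.5% at 120 per arm, 61% at 40 and 73% at 20.

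**The case against.** The strongest reply is that the awareness analysis is handed to the parent-study methods. In the protocol these include a PSF-vs-SOC main effect at each post-baseline time point and, for other smoking outcomes, a repeated-measures model: "Treatment conditions, time and the interaction of time with the treatment conditions will be included in the model". Listing baseline, week 12 and week 36 gives the time points and does not exclude the arms. This stands in part: a reader might infer that the plan commits itself to an uncontrolled before-after test, and the documents do not support that. What remains is that no contrast is named. The parent methods are themselves not one method: the protocol uses a mixed model with contrasts, while the SAP uses separate logistic regressions. The alcohol-use sentence has no such deferral.

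Three other inferences go too far:

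- **That the sub-study declares itself uncontrolled.** The statement "There will be no group assignment or randomization" most naturally describes the one-time interviews and focus groups. The awareness questions are asked at visits of the randomised trial.
- **That PSF vs SOC gives an unbiased estimate of what the new material does.** It estimates the whole updated eight-session programme against brief advice. PSF already taught tobacco-cancer risk before the update. Isolating the addition would mean comparing old with updated PSF, which were not randomised against each other.
- **That a known share of PSF participants missed the new material.** The sub-study came in by modification, apparently after enrolment began, but the roll-out date is not given. People whose baseline preceded the added questions have no baseline answers and could not enter a before-after comparison.

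It is also fair to say that Aim 2 calls itself preliminary.

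**Conclusion.** The point holds as an unspecified contrast attached to a causal claim. The only comparison written for awareness is baseline to follow-up, alcohol use is simply tracked over time, and change in both is to be read as due to the updated syllabus. If a before-after test were used, a modest common drift would often be declared a syllabus effect: about 52-69% of the time under the assumed 10-point rise with 120 participants, and less often with fewer. The drift and discordance are assumptions; only the 120 comes from the protocol.

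That SOC participants answer the questions is inferred from their placement at the parent-study visits and from the reference to the study sample. It is the natural reading, but it should be confirmed.

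Severity is minor. No primary endpoint, treatment or safety matter depends on it. It is a cheap improvement.

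**What to change.** State in the sub-study analysis section, and in the SAP, that the test for awareness and for alcohol use is the baseline-adjusted PSF-vs-SOC difference at weeks 12 and 36, from an arm-by-time model adjusted for drug arm. Restrict it to participants randomised after the updated syllabus came into use who have baseline answers. Both conditions are fixed by randomisation, so the randomised comparison is preserved, apart from missing follow-up.

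Record the syllabus version or its date of use for each participant. The protocol describes the updating as iterative, so each revision should be dated. Describe the result as the effect of the updated PSF package versus brief advice, not of the added material alone. Report before-after change descriptively, and reword the sentence that attributes changes in drinking to the syllabus.

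The cost is analysis wording and one variable, with no new data collection if SOC participants are asked the questions. The real price is precision: the number randomised after the update should be stated with the detectable difference it allows, which may be large.
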